12.4 Statistical Analysis Plan

Patient demographic and baseline characteristics, including age, gender, medical history, and prior therapy, will be summarized using descriptive statistics. For continuous variables, descriptive statistics (number [n], mean, standard deviation, standard error, median, and range will be provided. For categorical variables, patient counts and percentages will be provided.

Observed toxicities will be summarized, in terms of type, grade, time of onset, duration, and attribution to the study treatment. The overall response rate and complete response rate will be calculated along with the Clopper Pearson binomial 95% exact confidence intervals. Duration of response will be calculated using Kaplan-Meier product limit estimator; median duration of response will also be estimated when possible.

The miRNA/mRNA expression profile data will be summarized by descriptive statistics. The data will also be used to explore the miRNA/mRNA that show significant differences between responders and non-responders after leflunomide treatment. For miRNA/RNA profiling, fold changes >3 with an FDR <0.05 will be considered significant.

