10.0 STUDY CALENDAR

Table 10 describes required procedures. All procedures may increase in frequency if clinically indicated or oriented following toxicity. Adjustments to the treatment cycle due to a hold in study agent are detailed in [Section 5.2](#).

Table 10.0 Study Activity Calendar

	Screen -ing ^a	Cycle 1, 2, 3		Cycle 4+ Day 1 ^d	End of Treatment ^e				Active Follow-Up ^j
		Day 1 ^b	Day 14 ^c		Day 0 ^f	Days 1-11 ^g	Day 14 ^h	Day 30 ⁱ	
Informed Consent ^k	X ^s								
Inclusion/Exclusion Criteria ^l	X								
Registration ^m	X ⁿ								
Medical history ⁿ	X								
Physical exam	X	X		X				X	
Vital signs ^o	X	X		X				X	
Adverse events assessment ^p		X	X	X	X	X		X	
Concomitant meds review	X	X		X	X			X	
ECOG status (Appendix A) ^q	X	X		X				X	
Pregnancy test ^q	X								
TB antigen test ^r	X								
Hepatitis A, B, C testing	X ^s								
Skin photographs ^t	X	X		X	X			X	X
mSWAT ^u	X	X		X	X			X	X
Skin biopsy ^v		X ^w		X ^w				X ^w	
CBC with differential ^x	X	X	X	X				X	X
Chemistry panel ^y	X	X	X	X				X	X
Response assessment ^z		X		X	X			X	X
Teriflunomide clinical testing ^{aa}				X			X ^{dd}	X ^{dd}	
Leflunomide administration ^{bb}		Daily							
Cholestyramine ^g						X ^g			

- a. All screening procedures to be performed within 21 days of start of study agent except informed consent, acute hepatitis panel, skeletal survey which may occur within 30 days of start of treatment (footnote u) and except for registration which must occur within 7 days from start of treatment (footnote n).
- b. Day 1 assessments to be performed within 5 days (120 hours) prior to Day 1 drug (except footnote u for C1 only). Day 1 safety assessments must be resulted and reviewed prior to administration of agent for the cycle that is initiating. Screening assessments, if performed within this aforementioned time frame, may serve as C1D1 assessments. Note: items with footnote "aa" are not performed for C1D1; the windows for screening assessments still apply.
- c. Day 14 evaluations have +/- 3 day window.
- d. Day 1 assessments to be performed within 5 days (120 hours) prior to Day 1 drug. Day 1 safety assessments must be resulted and reviewed prior to administration of agent for the cycle that is initiating.
- e. Reasons to end study treatment include disease progression and unacceptable toxicity. See Section 5.8 for all criteria.

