- f. End of Treatment (EOT) Day 0 is defined as the day the determination to end treatment is made. EOT Day 0 assessments to be performed as soon as feasible, especially in the event of off treatment due to unacceptable toxicity and no later than 7 days after decision to end treatment; assessments performed after last dose of study agent(s) and within 7 days of the decision to end treatment may serve as EOT Day 0 assessments.
- g. EOT Day 1 is defined as the day cholestyramine administration begins; it will usually follow immediately after EOT Day 0, although it will not be deviation if this does not occur. If it does not follow immediately after EOT Day 0, the rest of calendar will follow per the actual EOT Day 1 (not EOT Day 0). Cholestyramine (8 grams three times daily for 11 days) will be administered according to [Section 5.5](#).
- h. EOT Day 14 assessments must occur after completion of cholestyramine, and may occur on Day 14 +/- 3 day window. If the cholestyramine administration period is extended beyond 11 consecutive days, the EOT Day 14 assessments may occur outside of this defined window.
- i. EOT Day 30 visit has a +/- 2 day window, however this window may be adjusted without deviation to ensure that it corresponds to the final teriflunomide clinical test (see footnote ee). All participants will be followed until resolution or stabilization of any serious adverse events occurring during treatment or starting within 30 days of last study drug administration or within the time to complete the EOT Day 30 assessments, which every occurs later.
- j. Active follow-up will occur for participants who have completed EOT procedures and yet to demonstrate disease progression. Disease response will be assessed every 3 months. Active follow-up will continue for 12 months or until disease progression, whichever is earlier.
- k. Informed consent process to be fully documented: e.g. prospective participant had sufficient time for deliberation, all questions were answered, treatment options provided by MD, full study reviewed including risks, and a copy of signed consent given to participant.
- l. Inclusion/exclusion criteria are detailed in [Section 3](#).
- m. See [Section 4.3](#) for slot reservation and registration process. Treatment must begin within 7 days of registration. Documentation providing Investigator's confirmation that all eligibility criteria are met must be available prior to registration.

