- n. Medical history to include review treatment history for CD30+LYPD medical history pertaining to eligibility, and demographic information.
- o. Vital signs: Weight, heart rate, blood pressure, respiration rate, temp. Height required only at baseline.

- p. Adverse event (AE) reporting begins for events that occur after start of study agent. AE recording and reporting will continue until the completion of the EOT Day 30 visit or until resolution or stabilization of any serious AE occurring before the completion the EOT Day 30 assessments, which every occurs later.
- q. Serum or urine pregnancy test for women of child bearing potential only.
- r. T-Spot or other TB antigen test.
- s. Consent, acute hepatitis panel, to be completed within 30 days prior to registration.
- t. Skin photographs: for subjects with skin lesions, up to five designated index lesions, representative of the subject's extent of disease, will be selected at baseline and measured and photographed using a digital camera. Photos should be taken against a blue backdrop. The photos will be taken on Day 1, prior to the first dose and then Cycle 2 Day 1 (-7 days) then every Cycle. In addition, half-body global photos (waist to feet, waist to top of head and sides) will also be obtained. Photos must be labeled with patient's protocol number and initials.
- u. Modified Severity Weighted Assessment Tool (mSWAT)[30] ([Appendix C](#))
- v. skin biopsies for research will not be taken at baseline if patients have a recent biopsy taken containing needed information.
- w. skin biopsies for research at baseline, at C2D1, C5D1, and EOT (if lesions are present), and at disease progression ([Section 9.2](#)).
- x. CBC with differential: erythrocytes (RBC), hemoglobin, hematocrit, platelets, total WBC plus absolute differential counts (neutrophils, lymphocytes, monocytes, eosinophils, basophils).
- y. Serum chemistry panel: Comprehensive metabolic panel (sodium, potassium, chloride, carbon dioxide, creatinine, urea nitrogen, calcium, glucose, albumin, total bilirubin, alkaline phosphatase, total protein, ALT/SGPT, AST/SGOT) LDH, magnesium, phosphorus, and uric acid.
- z. See [Section 11.2](#) for response assessment criteria.
- aa. Teriflunomide clinical blood assay to be ordered as "leflunomide metabolite" miscellaneous clinical test.

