14.3 Expedited Reporting

The table below indicates what events to report to expeditiously (Table 14.3).

Table 14.3 Expedited Reporting Guidelines

Time point	What to report
From signing of the consent to study completion	
• All UPs and AEs that meet the definition of a UP
For the time period beginning at treatment through 90 days following cessation of treatment, or 30 days following cessation of treatment if the subject initiates new anticancer therapy, whichever is earlier	
• All SAEs regardless of relationship to protocol therapy• All AESIs, overdose• AESIs (Section 14.2)- irAEs, overdose

All reportable events will require follow up until stabilization or resolution per the agreement of the Study PI.	
From Day 1 of protocol therapy up to 90 days post-last leflunomide dose	
• Pregnancies and lactation
Post Safety follow-up to removal from study	
• All SAEs that are at least possibly related to leflunomide.
NOTE: All events reported expeditiously require follow-up reporting until the event is resolved, stabilized, or determined to be irreversible by the investigator.	

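### The study calendar stops recording new serious adverse events at EOT Day 30, but sections 14.2 and 14.3 require them for longer

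*Combined protocol and SAP*

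**What the plan says.** Toxicity is a secondary objective (section 1.2). Section 12.4 states: "Observed toxicities will be summarized, in terms of type, grade, time of onset, duration, and attribution to the study treatment". It sets no time limit. Section 12.3 says which patients count (those with at least one dose), not which events.

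Four places govern the capture of late SAEs:

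- **Section 10.0, footnote p:** "AE recording and reporting will continue until the completion of the EOT Day 30 visit". The only extension is to follow an SAE that began before that visit was completed.
- **Table 10.0:** the row "Adverse events assessment" is marked on treatment and at EOT Days 0, 1-11 and 30. It is blank under Active Follow-Up. That column does carry photographs, mSWAT, CBC, chemistry and response assessment. Footnote j says of this period: "Disease response will be assessed every 3 months", for up to 12 months.
- **Section 14.2:** adverse events are collected until study participation ends. The CRF takes grade 2 or higher events from treatment through EOT, and all SAEs. Anything reported by an expedited route must also enter the routine data.
- **Table 14.3:** all SAEs, whatever the cause, are reportable "For the time period beginning at treatment through 90 days following cessation of treatment", cut to 30 days if new anticancer therapy starts. After the table's safety follow-up, and until removal from study, the duty narrows to "All SAEs that are at least possibly related to leflunomide".

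**The concern.** For a new SAE that begins after EOT Day 30, footnote p and section 14 cannot both be followed. The calendar is what staff work from at each visit, and it closes recording and schedules no question while a reporting duty is still running. Whether such an event reaches the database then depends on someone volunteering it.

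The protocol gives reason to care about late events. Section 2.2 notes that without the elimination procedure the metabolite can take up to two years to become undetectable. Section 6.1 lists rare but serious hepatic, pulmonary and malignant events, and section 14.4.2 makes second malignancies subject to expedited reporting. Against this, every patient is to receive cholestyramine and have levels checked, so late exposure should be limited.

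At stake is the completeness of a descriptive safety summary in 12 to 14 uncontrolled patients.

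**Working it through.** **The plan's own figure.** The only adverse event figure in the plan is the 86% chance in section 12.2 of seeing at least one affected patient among 12 when true incidence is 15%. 1 - 0.85^12 = 0.858, so it reproduces. It is not in dispute and does not depend on the recording window.

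**The rules side by side, for a new SAE:**

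| Onset | Footnote p | Section 14.2 | Table 14.3 |
|---|---|---|---|
| By EOT Day 30 | record | record | report, any cause |
| After EOT Day 30, to day 90 after treatment | do not record | record while on study | report, any cause, unless new anticancer therapy has started |
| After day 90, to removal | do not record | record | report if at least possibly related |

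The last row assumes that safety follow-up, which Table 14.3 does not define, ends at day 90. Sections 14.2 and 14.3 can be read together: the first governs what enters the CRF, the second what is expedited. Footnote p fits neither.

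**Length of the gap, longest case** (13 cycles of 28 days, then 12 months of active follow-up):

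- End of treatment: 13 x 28 = day 364.
- Footnote p stops: 364 + 30 = day 394.
- All-SAE row of Table 14.3 ends: 364 + 90 = day 454. Gap: 454 - 394 = 60 days.
- Active follow-up ends: 364 + 365 = day 729. Further gap, possibly related SAEs: 729 - 454 = 275 days.
- Total under these assumptions: 60 + 275 = 335 days, with no adverse event assessment scheduled.
- Existing follow-up visits: 12 months / 3 months = about 4.

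The day counts are approximate. EOT Day 30 is counted from the start of cholestyramine and may move to match the final teriflunomide test. If it moves later, the 60 days shrink.

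**Patient who progresses on treatment.** Sections 5.1 and 5.8 give no active follow-up and allow removal after the EOT assessments. If the 90-day row survives removal, the gap is 90 - 30 = 60 days with no study visit. If the row ends at removal, or if new anticancer therapy starts (30 - 30), it is 0 days. Table 14.3 does not say whether the row survives removal.

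**Weight of one event.** One patient is 1/14 = 7.1 to 1/12 = 8.3 percentage points. This holds for any event in a trial of this size. The documents give no expected rate of late SAEs.

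**The case against.** The strongest reply is that late SAEs would probably surface anyway. Patients in active follow-up are seen every three months with CBC and chemistry, including transaminases and bilirubin, and the first such visit falls close to day 90. Table 13.3 allows an adverse event form to be triggered by notification as well as by assessment. Section 14.3.1 defers to an institutional policy that is not in the documents. Section 12.4 already reports time of onset and attribution, so a recorded late SAE would be recognisable as late. All of this stands, and it keeps the point minor. It does not remove the conflict: laboratory tests do not ask about hospital admissions, and footnote p tells staff that recording has closed.

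A reader might infer more than the documents support:

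- **That footnote i also caps SAE reporting.** Its wording, "any serious adverse events occurring during treatment or starting within 30 days of last study drug administration", defines which SAEs must be followed until they resolve or stabilise. It does not limit the reporting of new ones.
- **That the start of the window matters equally.** Footnote p says "Adverse event (AE) reporting begins for events that occur after start of study agent", while section 14.2 starts at consent. But toxicity is evaluated only in patients who took at least one dose, an event before that dose cannot be a leflunomide toxicity, and before treatment Table 14.3 asks only for unanticipated problems.
- **That non-serious events are affected.** Footnote p and the CRF list in section 14.2 essentially agree for these.
- **That section 12.4 needs a new-or-worsened rule.** The baseline definition in section 7.1.1 serves dose modification. Extending it to the toxicity summary would be a preference, not a correction.

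**Conclusion.** The point holds as a minor inconsistency with a practical effect on safety capture. After EOT Day 30 the calendar neither records nor asks about new SAEs that sections 14.2 and 14.3 require. The gap is roughly 60 days for all SAEs, or none where new anticancer therapy has started, and then up to about 275 days for possibly related SAEs. These figures assume that safety follow-up ends at day 90, that EOT Day 30 falls about 30 days after the last dose, and, for the longest case, a full course of treatment and follow-up.

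The documents do not show that any SAE will be lost, only that its capture in this period rests on notification. The response analysis, the sample size and the dose modification rules are unaffected.

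**What to change.** 1. Amend footnote p so that new SAEs are recorded until study participation ends, as in section 14.2, with expedited reporting as in Table 14.3. Define in that table when safety follow-up ends.
2. Mark an SAE query in Table 10.0 at the existing three-monthly Active Follow-Up visits.
3. For patients removed after EOT because of progression, either state that the 90-day row of Table 14.3 ends at removal, or make one telephone SAE query at day 90.
4. In section 12.4, list SAEs with onset after EOT Day 30 separately from the main toxicity summary. They are collected less intensively, and the expedited route narrows to possibly related events, so pooling them would blur the attribution figures.

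The cost is a few lines of wording, one question at about four visits that already take place, a short extra listing and, if that option is chosen, one telephone call for patients who progress on treatment. No new clinic visits or tests are needed. The change is best made before follow-up data accumulate, because SAEs that nobody asked about may be hard to recover.

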
Leflunomide will be administered orally at a dose of 20 mg/day following a loading dose of 100 mg/day for the first three days of administration. Patients will be treated in planned 28-day treatment cycles. Patients may continue to receive cycles of treatment on study (maximum 13 cycles) until disease progression or unacceptable toxicity, or other criteria for removal from study treatment are satisfied. While on active treatment patients will undergo evaluation for response after every cycle. At the time of terminating leflunomide, all participants will receive 11 days of oral cholestyramine treatment (8 g three times daily) to reduce the plasma leflunomide levels. Patient will be followed for 1 year after terminating leflunomide treatment, or until disease progression, whichever is earlier.
	
Objectives	

Primary Objective
 
• To evaluate overall response rate of leflunomide treatment 
Secondary Objectives
 
• To assess complete response rate and duration of response of leflunomide treatment• To assess toxicities of leflunomide treatment• To assess disease status by the CAILS (composite assessment of index lesion severity) 
Exploratory Ex-vivo and Molecular Objectives
	

- To generate a preliminary RNA signature associated with response of CD30+LYPD to leflunomide

Study Design

This study will be conducted as a single center, single agent pilot study.

Evaluation Criteria and Endpoints

Primary Endpoint(s):

- The primary endpoint is overall response (CR + PR). Response will be categorized by mSWAT. The response categories and criteria are summarized in Table 11.2 of the protocol.

Statistical Considerations

Sample size: This study will accrue 12 response evaluable patients, with a maximum accrual of 14 patients. Because this is a rare disease that has not been systematically studied in a prospective clinical trial, there is a lack of historical data on the response rate (and by modified severity weighted assessment tool [mSWAT]) in this patient population. The sample size for this pilot study was chosen based on feasibility considerations, and not based on any definitive statistical criterion.

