With 12 patients, the 95% exact binomial confidence interval for the overall response rate will have a width of 55% (33% response rate, with 4 responders), 57% (42% response rate, with 5 responders), 58% (50% response rate, with 6 responders), 57% (58% response rate, with 7 responders), 55% (67% response rate, with 8 responders), 52% (75% response rate, with 9 responders), and 46% (83% response rate, 10 responders) respectively. For any AE with a true incidence of 15% or higher, with 12 patients there is at least an 86% chance of observing 1+ patients with such AE.

We project to accrue approximately one patient every 3 months. The projected study accrual duration is therefore 3 years.

Analysis: Observed toxicities will be summarized in terms of type (organ affected or laboratory determination), severity, attribution, time of onset, duration, serum concentration of the active leflunomide metabolite, probable association with the study treatment and reversibility or outcome. Baseline information (e.g. the extent/type of prior therapy) and demographic information will be presented as well to describe the patients treated in this study.

Rates and 95% Clopper Pearson binomial confidence interval (CI) will be calculated for overall response rate (patients that have confirmed CR or PR) and clinical benefit rate (patients that have confirmed CR/PR/MR or SD). In addition, sub-analyses will be performed where participants will be considered evaluable for response if they are confirmed eligible, receive at least 75% of leflunomide during the first cycle of therapy and have their disease re-evaluated. Response rates will also be explored based on number/type of prior therapy(ies) and serum concentration of the leflunomide metabolite (μ g/mL). Time to response and survival will be estimated using the product-limit method of Kaplan and Meier.

Preliminary molecular profiles for mRNA will be derived from skin biopsies. These profiles will be used to identify molecular correlates of therapeutic response using pathway identification and supervised principal components analysis.

Abbreviated Eligibility Criteria

Main Inclusion Criteria

- Adult patients with a diagnosis of CD30+LYPD with life expectancy of > 3 months
- ECOG ≤2
- Relapsed or refractory to at least 1 prior line of therapy
- Platelet count \geq 50,000/ μ L, ANC \geq 1000/mm³, AST and ALT < 2.0 x ULN, total bilirubin < 1.5 x ULN

Main Exclusion Criteria

- Prior treatment with lenflunomide

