Transcriptomic diversity exists within the clonal tumor cells that comprise cutaneous lymphomas as noted by recent work in mycosis fungoides and Sézary Syndrome [24, 25]. This correlates with the clinical experience of many experts that monotherapy alone is unable to produce response rates higher than 30-40% or meaningful durations of response in these patients as well. In addition, it is not only the tumor heterogeneity but also the response to the tumor in the microenvironment in the form of T-cell exhaustion that contributes to a lack of higher response rates [26]. For these reasons, it is important to assess the heterogeneity of gene expression of tumor cells and the cells of the microenvironment that likely exists within CD30+LYPDs. Single-cell RNA analysis provides a view of all involved cellular components simultaneously and their individual gene expression states. Utilizing single cell mRNA sequencing will not only allow us to note the multiple mutations and the molecular signature of this group of diseases for the first time by assessing the baseline biopsies, but also will help us to explore the mechanism by which the leflunomide suppresses the growth of the CD30+LYPDs as noted in work conducted on CTCL lines by the [name] group. In addition, this will contribute to determining what future combination therapies can be utilized for better clinical and durable response as well as for tailoring patient-specific treatment.

The parallel assessment of immunohistochemistry will allow us to correlate the new single cell data with what is seen/noted pathologically. Tumor cells in CD30+LYPD will be characterized utilizing a standard immunohistochemistry panel which includes CD3, CD4, CD8, CD30, BF1, Gamma, TRAF1, MUM1, perforin, granzyme, TIA-1 [27]. Current work in this area has noted that the predominant cells in the tumor microenvironment of CD30+LYPDs include a large percentage of CD163+ macrophages (M2) (44.7% in LyP vs. 35% in pcALCL). However, there are a number of tumor infiltrating CD8+ lymphocytes, FOXP3+ T-regulatory cells (Tregs) and only a few programmed cell death (PD1) lymphocytes [28]. We would like to examine the effect leflunomide has on the changing microenvironment as well.

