9.2.7 Immunohistochemistry

In addition, immunohistochemistry will be performed on all specimens to better examine the effect leflunomide has on the changing tumor and tumor microenvironment as well as correlate these findings with those from scRNA-seq. Current work in this area has noted that the predominant cells in the tumor microenvironment of CD30+LYPDs include CD163+ M2, tumor infiltrating CD8+ lymphocytes, FOXP3+ Tregs and programmed cell death (PD-1) lymphocytes.

The multiplex immunohistochemistry of the tumor microenvironment will distinguish the CD30+ T cells (tumor cells) from other cells (M2, Tregs, tumor infiltrating T cells) and whether or not PD1 co-expression is noted. The findings will be correlated to clinical response.

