12.2 Sample Size and Accrual Rate

This study will accrue 12 response evaluable patients, with a maximum accrual of 14 patients. Because this is a rare disease that has not been systematically studied in a prospective clinical trial, there is a lack of historical data on the response rate (and by mSWAT) in this patient population. The sample size for this pilot study was chosen based on feasibility considerations, and not based on any definitive statistical criterion. With 12 patients, the 95% exact binomial confidence interval for the overall response rate will have a width of 55% (33% response rate, with 4 responders), 57% (42% response rate, with 5 responders),

58% (50% response rate, with 6 responders), 57% (58% response rate, with 7 responders), 55% (67% response rate, with 8 responders), 52% (75% response rate, with 9 responders), and 46% (83% response rate, 10 responders) respectively. For any AE with a true incidence of 15% or higher, with 12 patients there is at least an 86% chance of observing 1+ patients with such AE.

We project to accrue approximately one patient every 3 months. The projected study accrual duration is therefore 3 years.

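### The responder RNA contrast and the metabolite exploration use only yes/no response in about 12 patients; the numeric mSWAT change, already collected, should be added as an outcome

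*Combined protocol and SAP*

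**What the plan says.** Two planned analyses relate a measurement to response as a yes/no outcome.

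- Section 12.4, RNA: "The data will also be used to explore the miRNA/mRNA that show significant differences between responders and non-responders after leflunomide treatment". Significance needs a fold change above 3 and an FDR below 0.05.
- Synopsis, Analysis paragraph: "Response rates will also be explored based on number/type of prior therapy(ies) and serum concentration of the leflunomide metabolite". Section 12.4 does not repeat this.

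The synopsis says of the endpoint: "Response will be categorized by mSWAT". Section 11.2 counts a patient as a responder if CR or PR is documented at any time on treatment. Appendix C defines mSWAT as a sum of body-surface percentages weighted 1, 2 and 4. The study calendar schedules it at screening and on Day 1 of each cycle, and section 12.1 has response assessed after every cycle. No analysis of the score or its change as a number is described.

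Two further analyses do not state their outcome scale. The synopsis says of the RNA profiles: "These profiles will be used to identify molecular correlates of therapeutic response using pathway identification and supervised principal components analysis". Section 9.2.7 says of immunohistochemistry: "The findings will be correlated to clinical response".

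On size, section 12.2 says: "This study will accrue 12 response evaluable patients, with a maximum accrual of 14 patients". It adds: "The sample size for this pilot study was chosen based on feasibility considerations, and not based on any definitive statistical criterion".

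**The concern.** Cutting mSWAT into responder and non-responder puts a patient just short of PR with one who worsened, and a bare PR with complete clearing. In a large trial that loss may be tolerable. With 12 patients it removes much of the information, and it makes the analysis depend on how many patients fall on each side of one cut.

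The exploratory objective is an RNA signature associated with response, and the background (sections 2.2 and 2.4) stresses wide variation in metabolite level and its link to response in rheumatoid arthritis. Since feasibility fixed the sample size, using the full outcome scale is one of the few ways to learn more from the same patients. The plan also has no rule for the case where one group is empty or nearly so.

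**Working it through.** **1. The plan's own figures.** Clopper-Pearson widths for 4 to 10 responders of 12 come to 55.2, 57.2, 57.8, 57.2, 55.2, 51.7 and 46.3%, matching section 12.2 (55, 57, 58, 57, 55, 52, 46%). The chance of seeing an AE of 15% incidence is 1 − 0.85^12 = 0.858, against the stated 86%. No power is stated for any association analysis, so there is nothing further to reproduce.

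**2. Inputs.** From the documents: n = 12. Assumed: a true response rate of 30, 40 or 50%; a correlation between one marker and mSWAT change of 0.3 to 0.8; a two-sided 5% level. Section 12.2 says historical response rates are lacking. The only background rate is in section 2.4, on cutaneous lymphoma generally: "monotherapy alone is unable to produce response rates higher than 30-40" percent. No document gives a correlation.

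**3. Power comparison by simulation.** Marker and mSWAT change are bivariate normal; a responder is a patient beyond the cut that gives the stated rate. Spearman correlation (t approximation) is compared with a pooled t-test of responders against non-responders, counted as no result unless each group has at least 2 patients.

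| Correlation | Spearman | t-test at 30 / 40 / 50% | Loss (points) |
|---|---|---|---|
| 0.3 | 14% | 10 / 11 / 11% | 4 / 3 / 3 |
| 0.5 | 34% | 22 / 25 / 25% | 12 / 9 / 9 |
| 0.6 | 50% | 32 / 36 / 37% | 18 / 14 / 13 |
| 0.7 | 68% | 44 / 50 / 52% | 24 / 18 / 16 |
| 0.8 | 86% | 60 / 68 / 70% | 26 / 18 / 16 |

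Using the exact Spearman critical value lowers its power by about 1 point.

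**4. Few responders.** P(0 or 1 of 12) = (1 − p)^12 + 12p(1 − p)^11.

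- p = 0.3: 0.0138 + 0.0712 = 8.5%
- p = 0.4: 0.0022 + 0.0174 = 2.0%
- p = 0.5: 13/4096 = 0.3%

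The chance of at most 2 responders is 25%, 8% and 2%.

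The smallest two-sided exact rank p-value with k responders is 2/C(12, k): 2/12 = 0.167 for k = 1 and 2/66 = 0.030 for k = 2. With k = 0 there is no contrast. The same holds in mirror image at 12, 11 and 10 responders.

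**5. Transcriptome-wide testing.** FDR control over many genes needs a much stricter per-gene level. At 0.001 and correlation 0.8, power is 35% for Spearman against 7-10% for the t-test. At 0.00001 (an assumption: one true hit among about 5,000 genes), Spearman has about 0.4%, 1% and 4% at correlations of 0.6, 0.7 and 0.8, and the t-test at most 0.3%.

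**The case against.** The strongest reply is that these analyses are exploratory, in a pilot that claims no power, and that sample size is the real limit. Step 5 bears this out for the RNA screen: on the plan's FDR rule, neither scale has useful power at n = 12. A continuous outcome does not rescue the transcriptome-wide search. What remains is the gain for metabolite level and for single or pre-selected markers.

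Second, the size of the loss depends on a correlation chosen by the analyst. That stands. At 0.3 both tests are weak and the loss is 3-4 points, so no single figure should be attached to this plan.

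Third, a reader might infer that all the biomarker work is dichotomised. The documents do not support that. The baseline-to-cycle-2 and malignant-versus-non-malignant comparisons in section 9.2.6 do not use responder status, and supervised principal components and immunohistochemistry leave the scale open.

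Fourth, a reader might infer that the comparison cannot be run with one responder. A pooled-variance t-test can be computed at 1 against 11; it is uninformative rather than impossible. Very uneven splits are also a concern mainly near a 30% rate, while section 12.2 tabulates observed rates from 33 to 83%.

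Finally, the fold-change rule applies to two groups and has no direct meaning for a continuous outcome. That is a reason to keep it with the responder display.

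**Conclusion.** The point holds for two analyses: the responder RNA contrast in section 12.4 and the exploration of response rates by metabolite level in the synopsis. Both use only a yes/no outcome although a numeric one is collected every cycle. For supervised principal components and immunohistochemistry, the gap is that the scale is not stated.

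The size is illustrative: about 13-26 points of power at correlations of 0.6-0.8, 9-12 at 0.5 and 3-4 at 0.3. It rests on normal variables, one marker, a 5% level, and correlations and response rates that the documents do not supply. The risk of 0 or 1 responder is 8.5% at a true rate of 30% and small at 40-50%.

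This is a cheap improvement to exploratory work. The primary endpoint and its confidence interval are unaffected.

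**What to change.** Leave the overall response rate as it is. In section 12.4 and the synopsis:

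- Add best percent change in mSWAT from baseline during study treatment as a continuous outcome, over the same period as the any-time response in section 11.2.
- Analyse it by ranks: Spearman correlation for metabolite level and for single markers, including immunohistochemistry.
- State that supervised principal components for expression uses this continuous outcome.
- Keep the responder/non-responder comparison, with its fold-change and FDR rule, as a companion display only when each group has at least 2 patients.
- Say that all these results are exploratory and that transcriptome-wide FDR significance is unlikely at n = 12 on either scale.

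The cost is wording and some programming, with no new visits, samples or patients. The main downside is that section 3 sets no minimum baseline mSWAT, and percent change is unstable when the baseline is low; ranks reduce that problem but do not remove it. Fixing the outcome scale before the data are seen also avoids choosing it afterwards.
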